Study Title: The Effect of Smart Ambient Bright Light for Nursing Home Residents with Alzheimer's Disease and Related Dementias (Smart Lighting Study)

PIs: [name] (Contact PI) and [name]

NCT05825404

04-24-2023

Data Analysis Plan

Aim 1: Pilot test the effect of SABL in reducing agitation in ADRD.

All data will initially be assessed with descriptive techniques to determine distributions and identify outliers. Baseline to post-intervention changes in participants' CMAI, NPI-NH, and ARS scores will be used as the outcomes in all subsequent analyses. To conduct the group analysis, each participant will serve as their own control, which allows minimal use of control variables. The effect of the intervention will be analyzed using multi-level modeling to adjust for clustering of participants at the facility level. We will use the daytime and nighttime average of lighting dosages (lux and CS) from the personal light monitors as the independent variable to analyze the effect of SABL on changes in CMAI, NPI, and ARS. Although not powered for a detailed analysis, we will explore the impact of participant characteristics (sex, age, race, ethnicity, ADRD stage, and daylight exposure) on the intervention effect by adding them as covariates to the regression model.

Aim 2: Evaluate the fidelity of the SABL delivery.

All data will initially be assessed using descriptive techniques to examine underlying assumptions and detect any violations. To assess the intervention fidelity, the lux and CS data measured via manual measurements will be analyzed using one sample t-tests to analyze lighting levels during the day and nighttime, compared to the target levels. The data from personal light monitors will be analyzed similarly at individual level. Although not powered for a detailed analysis, we will explore the impact of participant characteristics (sex, age, race, ADRD stage, co-morbidity, facility, and daylight conditions) on the lighting received based on the personal light monitor.

Aim 3: Evaluate the feasibility of implementing SABL.

The data includes ratings of acceptability, feasibility, and appropriateness. All data will be analyzed using descriptive analyses.

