1.0 Objectives

1.1 Study Objectives

Describe the purpose, specific aims or objectives. State the hypotheses to be tested.

Aim 1: Pilot test the effect of Smart Ambient Bright Light (SABL) in reducing agitation in persons with dementia. We will also examine the effect of SABL on other Behavioral and Psychological Symptoms of Dementia (BPSD), affect, and sleep and side effects. We hypothesize that participants will show less agitation and other BPSD and improve affect and sleep during and after SABL compared to baseline and control periods. We will also explore the intervention effect on residents' other behavioral and psychological symptoms and affect and monitor potential side effects.

Aim 2: Evaluate the fidelity of the SABL delivery. We will evaluate the fidelity of SABL delivery. We will measure lighting intensity (lux) and circadian stimulus (CS) levels via two methods: 1) on-site light measurements, and 2) a personal light monitor. We will compare the actual lighting dosage to our target lighting dosage.

Aim 3: Evaluate the feasibility of implementing the SABL. We will use convergent mixed methods to evaluate the acceptability, feasibility, and appropriateness of the interventions from perspectives of nursing home staff and administrators.

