1.2 Primary Study Endpoints

State the primary endpoints to be measured in the study.

Research typically has a primary objective or endpoint. Additional objectives and endpoints are secondary. The endpoints (or outcomes), determined for each study subject, are the quantitative measurements required by the objectives. Measuring the selected endpoints is the goal of a trial (examples: response rate and survival).

The primary outcomes of this study are 1) the effect of SABL on residents' agitation, other BPSD, affect, sleep and any side effects, 2) fidelity of SABL (e.g., lighting level on site and at individual level), and 3) feasibility of implementing SABL (e.g., acceptability, feasibility, appropriateness, time, and cost of implementing and maintaining the lighting).

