7.1 Study Design

Describe and explain the study design.

Aim 1: Pilot test the effect of SABL in reducing agitation in persons with dementia. This is a crossover, cluster randomized control trial to pilot test the effect of SABL in NHs. This design includes a 4-week intervention period and 2-week washout period. This design will allow for participants to act as their own control and thus reduce the needed sample size and strengthen the research rigor. The study procedures include five phases over 13 weeks. We will recruit a total sample of 40 nursing home residents with dementia and agitation from the 2 nursing homes, 20 residents from each nursing home. The two NHs will be randomly assigned into different sequences for intervention and control. Otherwise, the same study procedures will be

conducted simultaneously at the two NHs. During the daytime, participants will be guided and encouraged to spend time in the designated areas in the dining room and activity room for their meals and daily activities. For blinding prior to control period, we will perform installation procedures with non-SABL light bulbs. We will evaluate the effect of SABL on agitation, other BPSD, affect, and sleep, based on the actual lighting levels participants receive measured by personal light monitors. The study procedures include five phases: 1) baseline, 2) intervention, 3) post intervention/washout, 4) control, and 5) post control/washout. The sequence of intervention and control differs between the two NHs based on randomized assignment. Agitation and lighting will be measured at baseline and then once every two weeks throughout the study. We hypothesize that participants will show less agitation during and after SABL compared to baseline and control periods. We will also explore the intervention effect on other BPSD and affect and monitor adverse effects. **Aim 2: Evaluate the fidelity of the SABL delivery.** We will evaluate the fidelity of SABL delivery by measuring lighting intensity (lux) and CS levels in two ways: 1) on-site light measurements, and 2) a personal light monitor. The actual lighting data will be compared to the intended SABL design.

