We will evaluate resident participants' baseline agitation, BPSD, affect, and sleep, based on the residents' staff caregivers' inputs and observations of the residents. We will assess agitation, BPSD, affect, and sleep using the Cohen-Mansfield Agitation Inventory (CMAI), Neuropsychiatric Inventory-Nursing Home version (NPI-NH), Philadelphia Geriatric Center Affect Rating Scale (ARS), and Pittsburgh Sleep Quality Index (PSQI), respectively,

We will measure lighting level by 1) on-site manual light, and 2) a personal light monitor, LYS button during the baseline week. The LYS button is small (1 inch), light weighted (4g), and user friendly. It has a clip at the back of the button and can be easily clipped on clothes. For a resident who does not mind having the sensor placed on clothing, we may place it on the shirt collar or shoulder. We will communicate with their caregivers so that

they are aware of the button when clothes are being changed and make sure the button is clipped back on. We will check the device on site at least twice per week and will retrieve data after each week of data collection. We will pre-set a series of algorithms determining the device use status. If the device appears not to be placed or functioning properly, the system will send a warning message to the team and we will make all attempts to check the device on site. We will manually measure light level twice a week during the baseline week. In addition, we will place a personal light monitor, LYS button, on participants, all day, 7 days a week, during the baseline week.

Aim 3: Staff and administrators

1. Screening survey: We will ask participants to fill out the survey to confirm their eligibility. If they are eligible, we will continue to the next steps.
2. Baseline survey: we will ask participants to fill out a survey to collect data about their demographics and relevant work experiences (e.g., age, race, gender, education, and professional experiences).
3. Feasibility surveys: we will ask participants to fill out the Acceptability of Intervention Measure (AIM), Feasibility of Intervention Measure (FIM), and Intervention Appropriateness Measure (AIM) to evaluate the acceptability, appropriateness, and appropriateness of the SABL intervention.
4. Qualitative interview: their evaluation on the acceptability, feasibility, and appropriateness of the SABL lighting intervention.

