7.2.2 Visit 2 or Day 2 or Post-test, etc. (If applicable)

Provide a description of what procedures will be performed on visit 2 or day 2 or post-test in order of how these will be done. If your study involves more than two sessions or visits replicate this section for each additional session or visit (e.g., 7.2.3, 7.2.4, etc.). If your study involves only one session or visit, delete this section.

Aim 1:

Visits 2-6: After the intervention starts, we will measure agitation, BPSD, affect, and sleep, and intervention-related adverse effects using the CMAI, NPI-NH, ARS, PSQI, and adverse effect checklist once every two weeks.

Aim 2:

Visits 2-6: After light is installed, we will monitor the lighting by 1) on-site manual light measurements twice a week for 13 weeks, and 2) a personal light monitor, LYS button, placed on participants, all day, 7 days a week, every two weeks for 13 weeks.

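### Sleep and side effects are listed as primary outcomes, but the analysis sections plan no sleep estimate and no group summary of side effects by period

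*SAP*

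**What the plan says.** **Objectives and endpoints.** Protocol 1.1 hypothesises that participants will "improve affect and sleep during and after SABL compared to baseline and control periods". Protocol 1.2 gives as the first primary outcome the effect of SABL on "agitation, other BPSD, affect, sleep and any side effects".

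**Design and data collection.** Protocol 7.1 repeats the commitment for sleep: "We will evaluate the effect of SABL on agitation, other BPSD, affect, and sleep, based on the actual lighting levels participants receive". Sleep is measured with the PSQI at baseline (7.2.1). Follow-up measurement in 7.2.2 is made "using the CMAI, NPI-NH, ARS, PSQI, and adverse effect checklist once every two weeks". Table 2 in 7.2 gives the same set of measures at baseline and every two weeks.

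**Analysis.** Protocol 8.3 and the SAP share the same Aim 1 text. After an initial step ("All data will initially be assessed with descriptive techniques to determine distributions and identify outliers"), they state of changes from baseline to post-intervention that "CMAI, NPI-NH, and ARS scores will be used as the outcomes in all subsequent analyses". The light-dose model repeats the list: personal-monitor lux and CS are used "to analyze the effect of SABL on changes in CMAI, NPI, and ARS". Neither text mentions sleep, the PSQI, side effects or adverse events.

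**The concern.** The analysis text does more than leave out detail. It names three instruments and says that they serve for all later analyses. Read as a rule, it leaves out one hypothesised primary outcome (sleep) and one monitored primary outcome (side effects). The SAP and 8.3 use the same wording, so neither fills the gap for the other.

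Two things are at stake. First, the background in 2.2 presents better sleep as a step on the way from light to less agitation, so a positive or null CMAI result is harder to interpret without a planned sleep estimate. A sleep model chosen after the data are seen would be open to the charge of selection. Second, 2.2 itself criticises most earlier studies for saying nothing about side effects. Without a planned tabulation by period, this trial could leave its readers in the same position.

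**Working it through.** The plan gives no figure on this point. The only Aim 1 figure is the power of 0.92 in 8.2, which names no outcome, and nothing below depends on it. The check is a comparison of lists.

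**Step 1. Domains named, measured and analysed.**

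| Aim 1 domain (1.2) | Benefit hypothesised (1.1) | Effect to be evaluated against light received (7.1) | Instrument (7.2) | Outcome in 8.3 and SAP |
|---|---|---|---|---|
| Agitation | yes | yes | CMAI | yes |
| Other BPSD | yes | yes | NPI-NH | yes |
| Affect | yes | yes | ARS | yes |
| Sleep | yes | yes | PSQI | no |
| Side effects | no, monitored | no, monitored | checklist | no |

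Five domains are named and three are analysed, so 5 − 3 = 2 have no planned group analysis. Of the four with a hypothesised benefit, one (sleep) has no planned estimate.

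**Step 2. What the initial descriptive step covers.** It applies to all data, so PSQI and checklist data may be summarised. Its stated purpose is to look at distributions and outliers. It does not set SABL against control, and it gives no estimate of effect.

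**Step 3. Would adding the PSQI to the existing model be enough?** The hypothesis in 1.1 has two comparators: baseline and control periods. The model in 8.3 and the SAP takes change from baseline to post-intervention as outcome and light dose as the independent variable. As described, it has no SABL-versus-control-period term. Adding the PSQI to that model unchanged would therefore address only part of the sleep hypothesis.

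**Step 4. What is planned for side effects.** Protocol 18.2 compares an individual's symptoms with that person's baseline and non-intervention periods, considers other causes, and looks for the same symptom in other participants. Protocol 19.1.2 provides for checklist interviews every two weeks, logging and reporting. These are case-level steps. No section says that counts will be summarised by period across residents.

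**Step 5. What a fourth tested outcome costs.** Assume each outcome is tested at 0.05 (the level in 8.2, which does not say to how many outcomes it applies) and that the tests are independent. The chance of at least one false positive is 1 − 0.95^k:

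- k = 3: 1 − 0.857 = 0.143
- k = 4: 1 − 0.815 = 0.185

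The outcomes are probably positively correlated, in which case both figures are too high. The increase is the reason to rank the PSQI below CMAI and not beside it.

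**The case against.** **Sleep is not forgotten.** Protocol 7.1 commits to evaluating sleep against the light actually received, which is also the predictor in the SAP model. Hypothesis, instrument, schedule and predictor are all stated in advance. This stands, and it limits the post hoc worry to the choice of model and contrast. It also means that 7.1 and 8.3 disagree and have to be reconciled.

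**A reader might infer that the sleep data are collected and then not used**, and might count 40 residents × 7 visits = 280 PSQI assessments. The documents do not support this. The descriptive step covers all data. The product is also a maximum without attrition: 8.2 expects about 10% to drop out, and 7.2.2 labels the follow-ups as visits 2 to 6, although 7.2 gives six follow-up visits.

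**A reader might infer that side effects are never compared between SABL and other weeks.** That is too strong, because 18.2 makes such a comparison for individual residents. No side-effect hypothesis is stated, and the worsening of BPSD that is on the checklist can also show in CMAI and NPI-NH. What is missing is the group summary. The entry of not applicable under 9.7 is no evidence either way, because section 9 is required only for research above minimal risk.

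**This is a pilot.** A pilot need not be powered for every outcome. It should still say how it will estimate the outcomes that it calls primary.

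**Conclusion.** The point holds as an inconsistency between 1.1, 1.2 and 7.1 on one side and 8.3 and the SAP on the other. Followed as written, the analysis sections give no estimate or test for one of four hypothesised benefits, and no summary by period for the side-effect outcome. This rests on reading the outcome sentence as a closed list. The repetition of the same three instruments in the dose model supports that reading.

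The point should be corrected before analysis, but it does not threaten the agitation result: the CMAI analysis, the sample size and the data collection do not change.

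**What to change.** **Sleep.** Add the PSQI to the Aim 1 outcomes in 8.3 and the SAP. Specify a model that gives the SABL-versus-control-period comparison as well as change from baseline. State that the PSQI ranks below CMAI, and edit 1.2 to match, since 1.2 now calls sleep primary. Alternatively, remove sleep from the primary outcomes in 1.2 and from the hypothesis in 1.1, and bring 7.1 into line.

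**Side effects.** Add one table. For each checklist item, give the number of residents with at least one report in each period: baseline where collected, SABL, control, and the post periods. Tables 1 and 2 imply a baseline checklist, but the baseline list in 7.2.1 does not include it, so this should be settled. At most one overall SABL-versus-control comparison is enough. Section 10 describes these events as rare, so intervals for single items in about 36 to 40 residents would say little.

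**Cost.** One more secondary model, one more secondary test and one table. No extra residents or visits are needed.
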